#### 4.2.1 PRIMARY ENDPOINT

The primary endpoints (described below) of this mechanistic study are suicidal ideation and planning score differences between placebo days and stabilization days on the SITBI interview. These were chosen given their strong predictive validity in epidemiological studies.

- (1) Mean Within-Person Condition Difference (7 final placebo days – 7 final stabilization days) of SITB Suicidal Ideation subscale score
- (2) Mean Within-Person Condition Difference (7 final placebo days – 7 final stabilization days) of SITB Suicidal Planning subscale score

#### 4.2.2 SECONDARY ENDPOINTS

The secondary endpoints of this study include the daily telephone measures as follows:

- (6) Mean Within-Person Condition Difference (7 final placebo days – 7 final stabilization days) of BHI Hopelessness Score
- (7) Mean Within-Person Condition Difference (7 final placebo days – 7 final stabilization days) of CES-D Depression Total Score
- (8) Mean Within-Person Condition Difference (7 final placebo days – 7 final stabilization days) of UPPS-P Lack of Premeditation Impulsivity subscale
- (9) Mean Within-Person Condition Difference (7 final placebo days – 7 final stabilization days) of PROMIS Anxiety Total Score
- (10) Mean Within-Person Condition Difference (7 final placebo days – 7 final stabilization days) of SSES Social Evaluation/ Rejection Sensitivity subscale

#### 4.2.3 EXPLORATORY ENDPOINTS

None.

### 5 STUDY ENROLLMENT AND WITHDRAWAL

#### 5.1 PARTICIPANT INCLUSION CRITERIA

In order to be eligible to participate in this study, an individual must meet all of the following general criteria:

- Provision of signed and dated informed consent form
- Stated willingness to comply with all study procedures and availability for the duration of the study
- Ability to take oral medication and be willing to adhere to the medication regimen

To be eligible for participation, an individual must also meet all of these study-specific following criteria.

1. Must be biologically **female** and between the ages of **18-45 years**.
  - **Justification:** Women younger than 18 or older than 45 may have inconsistent menstrual cycles or may be postmenopausal and therefore no longer cycling.
2. Must have **normal menstrual cycles** between 25 and 35 days.
  - **Justification:** Abnormal menstrual cycle lengths or variability in lengths could introduce error variance into the experiment, and could reduce confidence regarding the timing of the experimental manipulation to cycle events.
3. Must be under the **current care** of an outpatient mental health provider.
  - **Justification:** Because we intend to recruit women with current suicidality, engagement with a mental health provider is required as a protective measure to ensure that participants have access to treatment if needed.
4. If the woman has children, she must be at least **1 year postpartum**.
  - **Justification:** The postpartum period can be characterized by altered hormone levels and changes; therefore, postpartum women may introduce error variance into the experiment.
5. Must be of **normal weight** (BMI between 18-29 kg/m^2); measured at the enrollment visit.
  - **Justification:** Responses to doses of hormones may vary by BMI and risk for thromboembolic events with hormone use increases in obese women.
6. Must report **at least some recent suicidal ideation (in the past month)** at enrollment.
  - **Justification:** As reviewed in the research strategy, the purpose of the study is to examine the impact of natural perimenstrual hormone withdrawal (vs. prevention of hormone withdrawal/stabilization of E2/P4) on within-person changes in suicide risk. The present sampling strategy **ensures generalizability** of our findings to clinical populations of interest and will also **prevent a floor effect** (i.e., zero-inflation of daily outcome measures and associated limitations in power to detect effects) on primary daily outcome measures (e.g., mediating behavioral constructs, suicidality).
7. Must be categorized as having **acceptably low imminent risk for suicidal crisis/attempt** according to established clinical and research guidelines (see Eligibility Table), which have been adapted for the current study in collaboration with the co-mentor, [name]. As co-mentor [name] notes in his 2014 methodological paper on research-based suicide risk assessment, evaluation of imminent risk of suicidal crisis/attempt is a complex clinical task, requiring integrative consideration of a variety of factors (including: general clinical presentation, ideation severity, frequency, recency, and associated consideration/intent; access to suicidal means; previous attempts and gestures; presence of suicidal planning, recent stressors, frequency of contact with mental health provider; and presence of social support). *Therefore*, our specific criteria for delineating whether a participant is eligible are based on an evidence-based determination that the participant is at **acceptably low imminent risk of suicidal crisis/attempt**. These decisions will be based on responses to a variety of questions from the SITBI and Severity of Suicidal Ideation Interview (clinical interviews at the beginning of an enrollment visit).
  - **Justification:** Individuals with current suicidality **are not necessarily at imminent risk for suicidal crises/attempt** (i.e., their risk is manageable on an outpatient basis through frequent clinical contact, such as the daily calls in the present study). Because the hormone protocol simply prolongs the physiologic luteal hormone profile, they are **not expected to expose participants to additional risk of suicidal crisis beyond what they would naturally experience during their typical monthly menstrual cycles**. However, out of an abundance of caution, we will

**exclude women with elevated imminent risk for suicidal crisis/attempt** (determined by structured interview and established guidelines). Individuals with histories of suicidality often have ongoing, habitual thoughts about death or suicide that are highly distinguishable from **imminent risk for suicide attempt**. In further support of this notion and of the feasibility of recruiting this population, it should be mentioned that up to 1/3 of the American population experiences suicidal ideation at some point in their lives, yet less than .01% die by suicide each year.

## **SPECIFICS OF SUICIDE RISK-RELATED ELIGIBILITY CRITERIA**

The study will **include only women with current suicidal ideation** (past-month endorsement of suicidal ideation) in order to maximize generalizability to our clinical population of interest. We hypothesize that *natural* perimenstrual withdrawal from ovarian hormones will be associated with significant but **transient shifts in continuously-estimated suicide risk that are not expected to escalate to the level of suicidal crisis/attempt** (due to the exclusion of certain women at highest risk for attempt, as noted below). In order to minimize the risk of suicidal crises during the study, we will **exclude women who meet evidence-based criteria for imminent risk of acute suicidal crisis/attempt**.

*The goal of these exclusion/inclusion criteria is to minimize the risk that a participating woman will demonstrate imminent risk of suicidal crisis/attempt during the study. The determination of acceptably low current risk of suicidal crisis/attempt will be carried out in multiple steps, as follows:*

1. First, women must pass a phone screen in which they will report on their previous psychiatric diagnoses and recent history of suicide attempts. At that juncture, the following criteria will be applied:
  - a. A woman will be excluded if she reports a suicide attempt or any concrete suicidal planning in the past 3 months, as the majority of repeated attempts occur within the first three months following an initial attempt.
  - b. A woman will be excluded if she reports a history of more than one suicide attempt, as multiple attempts represent a uniquely potent risk factor for additional suicidal crises/attempts.
  - c. A woman will be excluded (and referred) if she reports that she does not currently visit a mental health provider (psychiatrist, therapist) at least once every 3 months.
  - d. A woman will be excluded if she reports any extreme external stressors (e.g., death of a loved one, loss of employment) in the past month, as extreme stressors drastically increase the risk of suicidal crisis.
  - e. A woman will be excluded if she reports a history of clinical diagnosis with manic episode, psychotic symptoms, or substance use disorder, as these disorders reduce predictability and increase likelihood of suicidal crises/attempt.
2. Second, women must pass an in-person eligibility screening at the beginning of an enrollment visit, in which they will complete a clinical interview designed to more thoroughly assess the risk factors described in 1a-1e above, as well as additional determinants of suicide risk outlined in Eligibility Table.
  - a. Eligibility criteria in 1a-1e above will again be re-assessed and applied.
  - b. Using a clinical interview based on the SITBI interview and the Scale for Suicidal Ideation interview, the PI will evaluate each woman on a variety of risk factors for suicidal crisis and evaluate whether a woman has acceptably low imminent risk of suicidal crisis/attempt using the decision rules described in the leftmost column in Eligibility Table and summarized below:
    - ***The evidence-based determination of acceptably low risk of suicidal crisis/attempt will be based on the count of positive findings in each Row of Eligibility Table (see next page), as follows: No positive findings in Row 5; No***

***greater than 1 positive finding in Row 4; No greater than 2 total positive findings in Rows 3 + 4; No greater than 3 total positive findings in Rows 2, 3, and 4.***

3. Finally, [name] (the PI) will review the results of each eligibility visit interview with [name] at weekly meetings (see Training Plan and Co-Mentor Letter) to verify that the individual demonstrates acceptably low imminent risk of suicidal crisis/attempt before approving participation in the experiment. Should Drs. [name] and [name] determine the patient is at imminent risk of suicidal crisis/attempt despite meeting the criteria described previously, the patient will not continue with participation. However, should [name] agree that the patient indeed demonstrates acceptably low risk of suicidal crisis/attempt as outlined in Eligibility Table, the participant will continue with randomization and participation in the study.
4. *Note that ongoing participant suicide risk monitoring and management is described in later sections.*

## EXPERIMENTAL ELIGIBILITY TABLE

The goal of the suicide-related exclusion/inclusion criteria (outlined below) for the study is to **minimize** the risk that a participant will experience an acute suicidal crisis or attempt suicide during the study. Evidence-based criteria were developed in collaboration with the co-mentor, [name]. History of mania, psychosis, or substance abuse disorder will also be exclusionary. Table notes: Recent = In the past month. MHP = Mental Health Provider. SITBI items 3a, 3b, 4a, 4b, 4c. SITBI items 1a, 1b, 1c, 1f, 2c. SITBI items 2a, 2b.

ROW	Suicide Attempts 		Suicidal Thoughts 				Recency of Last Suicidal Planning 	Current Access to Means	Recent Stressors/Loss	Current Frequency of MHP Contact	Current Social Support
	Number	Recency	Recency	Recent Frequency	Recent Severity	Recent Intent					
1	Never	Never	In past year	Less than monthly	1f=1	2c=1	Never	No Access to Means	None	>1x/month	Multiple Strong Supporters
2 No more than 3 total positive findings allowed in Rows 2,3, +4	Any gesture or NSSI, no attempt	In past 2 years	In past month	~1x/month	1f=2	2c=2	>2 years ago		Extreme Stressors in past year	~1x/month	One Strong Supporter or multiple supports
3 No more than 2 total positive findings allowed in Rows 3 + 4	1 aborted attempt	In past year	In past week	~1x/ week	1f=3	2c=3	1-2 years ago	Access to Nonspecific or Unfeasible means	Extreme Stressors in last 3 months	~1/2 months	Very Limited Support
4 No more than 1 positive finding allowed in Row 4	1 attempt	In past 6 months	Now	>1x/ week	1f=4	2c=4	3 months to 1 year ago	Access to Specific, Feasible Means	Extreme Stressors in last 1-2 months	~1x/ 3 months	No Support
5 No positive findings allowed in Row 5	>1 attempt	In past 3 months					<3 months ago		Extreme Stressors in last month	<1x/ 3 months	

## 5.2 PARTICIPANT EXCLUSION CRITERIA

Any individual meeting any of the following exclusion criteria at baseline will be excluded from the study:

1. Must **not be pregnant, breastfeeding, or trying to become pregnant**. Pregnancy status will be confirmed using urine pregnancy test at the enrollment visit and again at the first visit of the second condition. Women will be encouraged to use a barrier method of birth control during the study.
  - **Justification:** Administration of ovarian hormones to a pregnant woman could negatively influence the pregnancy in a variety of ways, including risks to the health of the fetus.
2. Must not be taking any form of **exogenous hormones** or IUD, and must have ended previous use of hormonal preparations at least one month prior to the study.
  - **Justification:** The use of additional exogenous hormones poses safety risks and would undermine experimental control of hormones.
  - **Women will be required to use licensed barrier methods of contraception during study participation; if they are unable to commit to this responsibility, they will not be eligible for participation.**
8. Must report no personal history of any **chronic medical condition**, including but not limited to metabolic or autoimmune disease, epilepsy, endometriosis, cancer, diabetes, cardiovascular, gastrointestinal, hepatic, renal, or pulmonary disease, and no personal or first degree family history of thromboembolic events.
  - **Justification:** Administration of exogenous hormones to women with these chronic medical conditions may increase the risk of an adverse health-related response to hormones. Further, the purpose of the present study is to determine the impact of hormonal stabilization (vs. natural withdrawal) in otherwise physically *healthy* women.
9. Must not currently smoke **cigarettes**.
  - **Justification:** Administration of ovarian hormones to women who smoke may increase the risk of thromboembolic events.
10. Must not report a history of clinical diagnosis of postpartum depression or premenstrual dysphoric disorder (Note: PMDD diagnosis must have been made based on prospective daily ratings).
  - **Justification:** Some evidence would suggest that the pattern of perimenstrual symptoms that have been linked with these reproductive mood disorders *could* differ meaningfully from that which we expect in the more general clinical population of women with suicidality. Because these distinctions are not yet clear, women with a self-reported history of clinical diagnosis with these disorders will be excluded.
11. Must not report any history of manic episode, psychotic symptoms, or substance use disorder.
  - **Justification:** These factors are known sources of variability in suicidality and would therefore introduce error into our models as well as increasing the risk that a participant would experience a suicidal crisis during the study.

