## 7.2 LABORATORY PROCEDURES/EVALUATIONS

### 7.2.1 CLINICAL LABORATORY EVALUATIONS

A point-of-care urine **pregnancy test** will be completed in our laboratory on site on two occasions: prior to randomization at the enrollment visit, and at the third study visit of the first condition.

At all 6 laboratory assessments during active treatment with placebo or E2/P4, women will provide 10ml **blood samples** to be assayed for E2/P4 to evaluate the success of the hormone in achieving stable luteal phase levels of E2/P4. [name]'s laboratory at UNC will conduct assays. Storage onsite will be handled by medical technician [name] in [name] laboratory.

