#### 7.3.3 FOLLOW-UP

Following the baseline/enrollment visit, women will remain in contact with study staff and will begin ovulation testing as instructed. When ovulation testing is positive (day 0), the participant will contact the study staff to schedule the first three laboratory assessment visits (visits for condition 1) on days +7, +14, and +22. All laboratory assessment visits are identical in structure and content, with the singular exception that the third laboratory visit in the first condition will include a pregnancy test that must be negative prior to starting the second condition. When the first condition is completed and the second pregnancy test is negative at the third laboratory visit, women will again remain in contact with study staff to schedule ovulation testing in the next menstrual cycle. Once again, when ovulation is confirmed (day 0), the final 3 laboratory assessments (for condition 2) will be scheduled on days +7, +14, and +22. These visits may be scheduled up to +/-2 days in either direction.

- **Follow-Up Assessments Administered (see section 4.1 for Abbreviations):**

Variable	Interview Measure	Self-Report Measure	Task Measure
Vitals	-	-	Weight
Urine Pregnancy Screen (3 rd follow-up only)	-	-	X
Blood Sample (10 ml tube)	-	-	Serum E2/P4
Suicidality	Full SITBI	-	-
Depression	-	CESD	-
Hopelessness	-	BHI	FT-IRAP
Inhibitory Control	-	UPPS-P	SST
Threat Sensitivity	-	STAI	DPT
Negative Social Appraisals	-	SSES	SAR-IAT
Side Effects, AEs, and Compliance Monitoring	X	-	-

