**Follow-Up Timeline:**

**Condition 1 (Follow-Up Visits 1-3):**

- Negative Pregnancy Test Confirmed at Enrollment
- Ovulation Testing
- Positive Ovulation Test #1= Day 0
- Study Followup Visits 1-3 Scheduled for days +7, +14, +22
- Study Followup Visit 1 (Day +7): Assessments, administration of study agent patch A and dispensation of pills (**Condition 1**)
- Study Followup Visit 2 (Day +14): Assessments, replacement of study agent patch A with patch B (**Condition 1**)
- Removal of study patch and end of pills on day +21
- Study Followup Visit 3 (Day +22): Assessments, Pregnancy Test

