**Condition 2 (Follow-Up Visits 4-6):**

- Negative Pregnancy Test Confirmed at Visit 3
- Ovulation Testing

- Positive Ovulation Test #2= Day 0
- Study Followup Visits 4-6 Scheduled for days +7, +14, +22
- Study Followup Visit 4 (Day +7): Assessments, administration of study agent patch A and dispensation of pills (**Condition 2**)
- Study Followup Visit 5 (Day +14): Assessments, replacement of study agent patch A with patch B (**Condition 2**)
- Removal of study patch and end of pills on day +21
- Study Followup Visit 6 (Day +22): Assessments, Schedule Debriefing

---

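### The second pregnancy test is set at two different visits, and under either schedule placebo-first women have no test after E2/P4 starts

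*Combined protocol and SAP*

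**What the plan says.** Section 5.2, exclusion criterion 1: "Pregnancy status will be confirmed using urine pregnancy test at the enrollment visit and again at the first visit of the second condition". The follow-up timeline identifies that visit as Visit 4, where condition 2 treatment begins: "Study Followup Visit 4 (Day +7): Assessments, administration of study agent patch A and dispensation of pills". No test is named on that line.

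Section 7.2.1 provides for two tests: "prior to randomization at the enrollment visit, and at the third study visit of the first condition". Section 7.3.3 describes the laboratory visits as "identical in structure and content, with the singular exception that the third laboratory visit in the first condition will include a pregnancy test", and says that this test "must be negative prior to starting the second condition". The timeline agrees. Condition 1 has "Study Followup Visit 3 (Day +22): Assessments, Pregnancy Test" and condition 2 opens with "Negative Pregnancy Test Confirmed at Visit 3".

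After condition 2 dosing starts, no test is listed. The last laboratory visit reads "Study Followup Visit 6 (Day +22): Assessments, Schedule Debriefing". For the debriefing visit, 7.1.1 lists only the suicide-risk interview and 7.3.4 adds only referral for care. The early termination visit (7.3.5) repeats the debriefing interview. The schedule of events (7.3.7), as extracted, has no pregnancy-test row that could settle the matter.

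Section 5.2 gives harm to the fetus as its reason for excluding pregnant women. Section 8.4.5 sets out what follows a pregnancy: withdrawal, unblinding of the responsible physician, and clinical care including supervised discontinuation of hormones.

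**The concern.** There are two separate problems. First, the eligibility section and the procedures sections give different visits for the same safety test, all in current text. Staff working from one will run the test at a different visit from staff working from the other.

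Second, each version serves only as a check before condition 2. In the active-first order that check happens to fall after hormone exposure. In the placebo-first order it falls before exposure, and nothing later replaces it. Section 8.4.5 can act only on a pregnancy that is known. If a placebo-first woman conceives around the condition 2 ovulation, no scheduled test would reveal it before she leaves the study. The blood samples do not fill the gap: 7.2.1 has them assayed for E2 and P4 only, and 10.4.5 says that these assays are examined after the study closes.

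**Working it through.** No plan figure is at issue. The check sets the passages side by side and counts tests and days.

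**Inputs.** Placebo-first women receive E2/P4 at Visits 4-6, n=15 per order (schematic). Dosing runs from day +7 to day +21 and the third visit of each condition is on day +22 (timeline). Visit windows are ±2 days (7.1.1). Eligible cycle length is 25-35 days (5.1). The target is 30 completers from 45 women randomised (10.5). The LH surge precedes ovulation by 24-36 hours (4.1).

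**Step 1: count the tests.**

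| Order | Second test at | Tests between enrollment and condition 2 dosing | Tests after E2/P4 starts |
|---|---|---|---|
| Placebo-first | Visit 4 (5.2) | 1 | 0 |
| Placebo-first | Visit 3 (section 7) | 1 | 0 |
| Active-first | Visit 4 (5.2) | 1 | 1 |
| Active-first | Visit 3 (section 7) | 1 | 1 |

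The Visit 4 rows take the test to precede the patch, since the timeline lists assessments first.

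**Step 2: count the women.** The zero applies to 15 of 30 target completers. Among those randomised, 45 / 2 = 22.5, so 22 or 23 if allocation is 1:1. That is a ceiling, because placebo-first women who leave during condition 1 never receive hormones.

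**Step 3: timing.** Let L be the interval between consecutive positive ovulation tests, assumed equal to the eligible cycle length of 25-35 days.

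- Visit 3 test to the next positive ovulation test: L − 22 = 3 to 13 days.
- Visit 3 test to the first condition 2 dose: (L − 22) + 7 = L − 15 = 10 to 20 days. With both windows used, the shortest is (25 − 24) + 5 = 6 and the longest is (35 − 20) + 9 = 24 days.
- Visit 3 test to the last condition 2 dosing day: (L − 22) + 21 = L − 1 = 24 to 34 days.
- Visit 4 test (5.2) to the last condition 2 dosing day: 21 − 7 = 14 days.
- Active-first women, end of hormones to the second test: 22 − 21 = 1 day at Visit 3, or (L − 21) + 7 = 11 to 21 days at Visit 4, and longer if treatment delays the next ovulation.

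**Step 4: what a Visit 4 test could see.** Day +7 counts from the positive ovulation test, so Visit 4 falls 7 − 1.5 = 5.5 to 7 − 1 = 6 days after ovulation. The documents give no sensitivity for a urine test that early. Visit 6 on day +22 falls 20.5 to 21 days after ovulation and nominally one day after the last dose. Its window reaches back to day +20.

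**The case against.** The strongest reply is that the risk is already controlled. Section 5.2 excludes women who are trying to conceive and makes a commitment to barrier contraception a condition of eligibility. Section 7.3.3 requires both a negative Visit 3 test and a fresh positive ovulation test before condition 2. Daily calls and adverse-event questions may also bring a pregnancy to light. Most of this stands. Two qualifications apply. Section 5.2 also says, in criterion 1, that women are only encouraged to use a barrier method. And none of the routine contacts is a test.

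A reader might infer several stronger points that the documents do not support:

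- *That the conflict lets women start condition 2 untested.* It does not. A site that follows either version runs one test between enrollment and condition 2 dosing.
- *That the 10-20 days after Visit 3 are open exposure time.* A woman pregnant from condition 1 would not be expected to produce the new positive ovulation test. What remains is conception around the condition 2 ovulation itself.
- *That a Visit 4 test closes the gap.* Nothing in the documents shows that a test 5.5-6 days after ovulation would detect a conception in that cycle.
- *That a Visit 6 test protects against exposure.* Dosing has nominally ended by then, so supervised discontinuation under 8.4.5 is moot. Unblinding and clinical care are not.

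The table in 7.1.1 marks the urine screen for the third visit only. Read alone, that could include Visit 6. Sections 7.2.1 and 7.3.3 restrict it to the first condition, and the Visit 6 line names no test.

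**Conclusion.** The point holds in two limited parts. The protocol gives two different visits for the second pregnancy test, with 5.2 standing alone against 7.2.1, 7.3.3 and the timeline. And on either schedule no test follows the start of E2/P4 in placebo-first women, 15 of 30 target completers, while active-first women have one.

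This is a gap in safety scheduling. It does not touch the endpoints, alpha, power or sample size. No probability of an exposed pregnancy is claimed, because the documents give no conception rate. The counts of tests and women rest on the visit schedule alone. The day intervals rest on the assumption that the ovulation interval equals the eligible cycle length. The absence of a row in 7.3.7 is taken from the extracted text and is not relied on.

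**What to change.** Correct 5.2 to match section 7 and add one test. Suggested sentence: *Urine pregnancy tests are done at enrollment, at Visit 3 (the result must be negative before condition 2 begins), and at Visit 6 or the early termination visit.*

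Carry it through:

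- The 7.1.1 and 7.3.3 tables name Visits 3 and 6.
- Section 7.2.1 goes from two tests to three.
- The 7.3.3 text drops the claim of a single exception.
- The Visit 6 timeline line and 7.3.5 gain the test.
- Section 7.3.7 gains a pregnancy-test row.
- Section 8.4.5 says that a positive result at Visit 6 or early termination leads to unblinding of the responsible physician and clinical follow-up.

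The weaker contraception sentence in 5.2 can be aligned with the requirement in the same edit.

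A pre-patch test at Visit 4 is optional, for the reason given in Step 4. If pre-patch tests are adopted, Visit 1 needs one as well: 7.1.1 sets no fixed interval between enrollment and the first condition, and the timeline lists no test at Visit 1.

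Cost of the core change: one point-of-care urine test per woman, 1 × 30 = 30 at target and at most 1 × 45 = 45, at visits that already exist and with no new staff. Each optional pre-patch test adds one more per woman.
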